### **3.6.1.3 MR Imaging Period**

Prior to entering the MRI scanner the patient will answer the standard MRI safety checklist administered to all patients undergoing MRI in the Clinical Center to insure that it is safe to perform an MRI. The patient will be placed into the magnet in supine position and an intravenous line will be placed. A 32 channel cardiac coil will be used for MR imaging. An endorectal coil will be used for localized disease arm.

The following scans will be obtained:

- Scout view of the pelvis to check positioning of the cardiac coil.
- T1 weighted MRI of abdomen and pelvis.
- T2 weighted MRI of abdomen and pelvis.
- Total nominal time: 40 minutes +/- 5 minutes for setup and clean-up +/- 10 minutes in case any sequence needs to be repeated due to unforeseen events such as patient motion during imaging acquisition. At any given time the patient will be required to lie still for 5-7 minutes.

After completion of the pre-injection MRI scan, patient will have the Eovist® injection as detailed above in section [3.3](#). The patient will be assessed for adverse events 15 minutes post-Eovist® Injection and if they are stable, the same MR imaging protocol (except for the scout view) specified above will be performed immediately after injection and at approximately 10th, 20th and 60th minute time points after injection with the same MRI set up.

Following imaging acquisition, the data will be transferred to the clinical PACS system for storage.

### **3.6.1.4 Post-Eovist® Enhanced MR Imaging Period**

A final set of vital signs and AE assessment will be performed at the end of the 60 minute MRI scan.

Within 20 weeks of the Eovist® enhanced MRI the biopsy procedure will be performed.

### **3.6.1.5 Clinical Laboratory Evaluations**

The clinical laboratory variables assessed in this study are displayed in Table 1; they will be measured at the NIH Clinical Center laboratory.

**Table 1 Clinical Laboratory Variables**

Serum Biochemistry	Hematology
--------------------	------------

Alanine aminotransferase	Hematocrit
Albumin	Hemoglobin
Alkaline phosphatase	Platelet count
Aspartate aminotransferase	Red blood cell count
Bilirubin (total, direct)	White blood cell (WBC) count
Calcium	
Chloride	
Creatinine	
Glucose	
Potassium	
Sodium	
Urea nitrogen	
PSA	

Blood samples will be obtained for assessment of serum biochemistry and hematology parameters as described in the Study Calendar (Section 3.6). The maximum amount of blood taken for these tests will not be more than 60 ml.

Interpretation and follow-up of abnormal laboratory test results should be conducted in conjunction with the clinical situation of the subject and in consultation with the referring physician.

#### **3.6.1.6 Vital Signs**

Vital signs will be measured at various pre- and post-injection time points described in the Study Calendar. Vital sign parameters include measurements of systolic and diastolic BP, heart rate, temperature and respiratory rate.

The interpretation and follow-up of abnormal vital signs results should be conducted on a case by case basis in conjunction with the individual clinical situation.

#### **3.6.1.7 Injection Site Monitoring**

Injection site monitoring will be performed prior to administration of the imaging agent and at the 5th minute post-injection described in the Study Calendar (Section 3.6). Any abnormal findings during this period will be recorded as AEs on the research record. Abnormal injection site findings include, but are not limited to, pharmaceutical extravasation, bleeding, hematoma, redness and infection.

Any abnormal finding that is new or represents a worsening from baseline is an AE. Once AE notification is decided upon, investigators are required to follow the procedure described for AE notification and document the abnormal finding in the subject's research record.

#### **3.6.1.8 Pre-administration events**

The presence of any pre-administration event (baseline signs and symptoms present just before Eovist® administration) will be recorded in C3D

The following information will also be recorded:

- The date and time of evaluation
- The onset time
- The resolution time or duration
- Action taken
- Status of symptom
- Intensity

### **3.7 Surgical Guidelines**

As part of their standard of care for their disease, subjects will have biopsy within 20 weeks of Eovist® enhanced MRI. Pathologic specimens will be obtained for histological assessment. Further details are provided in Section [3.1.4](#).

In the event that the Eovist® enhanced MRI scan demonstrates an unexpected finding, it will be correlated with conventional imaging. While Eovist® enhanced MRI findings will not be used to direct therapy, the referring physician(s) will be made aware of any such findings, and may perform additional tests to clarify findings.

### **3.8 Radiation Therapy Guidelines**

The patient should not undergo radiation therapy to the target lesion between biopsy and Eovist® MRI imaging. However, clinically indicated radiation therapy cannot be delayed by the biopsy after Eovist® enhanced MRI.

### **3.9 Off-Study Criteria**

Patients will be taken off study once all study procedures are complete. In cases where a subject withdraws or is withdrawn from the study after administration of Eovist® and before biopsy is performed, a replacement subject will be enrolled.

Should a subject withdraw after administration of Eovist®, or should the investigators decide to withdraw the subject, all efforts will be made to complete and report the protocol-stipulated observations up to the time of withdrawal as thoroughly as possible. A final evaluation at the time of the subject's withdrawal should be made and an explanation given of why the subject is withdrawing or being withdrawn from the study. The reason and date and time of withdrawal must be recorded. If the reason for withdrawal is a clinical AE, monitoring will continue until the outcome is established.

#### **3.9.1 Criteria for Removal from Protocol**

- Investigators have the right to withdraw subjects from the study in the event of illness, AEs, or other reasons concerning the health or well-being of the subject, or in the case of lack of co-operation.
- Subject completes Eovist® enhanced MRI and has biopsy of the target lesion
- Patient requests to be taken off study
- Patient non-compliance with protocol guidelines

- Unacceptable treatment related toxicity as described in section **10.2.2**

Patient may not be taken off study until unacceptable toxicities have stabilized or resolved.

### 3.9.1.1 Off Study Procedure

Authorized staff must notify Central Registration Office (CRO) when a subject is taken off-study. An off-study form from the web site (<http://home.ccr.cancer.gov/intra/eligibility/welcome.htm>) main page must be completed and faxed to [contact].

## 4 CONCOMITANT MEDICATION/MEASURES

MRI contrast may be lessened by the following concomitant medications (OATP1B3 inhibitors)

- Select antibiotics (rifampicin, penicillin, ceftriaxone, cefmetazole, cefoperazone, and cefotaxime)
- Cyclosporin A
- Docetaxel / Paclitaxel
- Digoxin
- Fexofenadine
- Ibuprofen
- Imatinib
- Irinotecan
- Methotrexate

Any non-essential medications on the above list should be put ‘on-hold’ prior to the MRI for three days. Antibiotics should be finished before the MRI. If there is an essential medication that cannot be substituted then it will be noted but the patient will still be eligible for the study.

## 5 DATA COLLECTION AND EVALUATION

### 5.1 Data Collection

#### 5.1.1 Clinical Data

All data will be kept secure. Personal identifiers will not be used when collecting and storing data. An enrollment log will be maintained in the regulatory binder/file which is the only location of personal identifiers with unique subject identification number.

Clinical data including summary and demographic data will be collected and entered into NCI CCR Database, C3D. Adverse events occurring during any scanning session will be recorded. Adverse events which are designated possibly, probably or definitely related to Eovist® will also be recorded.

Imaging data will include storage of the reconstructed images and image derived parameters on a secure, password protected lab imaging database. The lab imaging database will be stored

and maintained in the Molecular Imaging Program facilities. Personal identifiers will not be used when storing data.

Non-Anonymized images may also be stored in the clinical center PACS.

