### **5.1.2 Safety Data**

The following safety data will be collected and evaluated according to the Study Calendar (Section 3.6):

- Clinical laboratory variables: serum biochemistry and hematology
- Injection site monitoring
- Pre-administration events (baseline signs and symptoms)
- AEs

SAEs will be recorded if they occurred as follows:

- After a subject first received Eovist® and throughout the subjects follow-up period,
- During the subject's follow up period, and for which a causal relationship to Eovist® cannot be ruled out.

Interpretation and follow-up of abnormal results will be done on a case by case basis in conjunction with the individual clinical situation. Any clinically significant abnormal finding, or change in one that represents a worsening from baseline, is an AE. Once a decision is reached to report a finding as an AE, the investigator is required to follow the procedure described for AE notification.

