### **9 SAFETY REPORTING REQUIREMENTS/DATA AND SAFETY MONITORING PLAN**

#### **9.1 Definitions**

##### **9.1.1 Adverse Events**

An adverse event is defined as any reaction, side effect, or untoward event that occurs during the course of the clinical trial associated with the use of a drug in humans, whether or not the event is considered related to the treatment or clinically significant requiring treatment. For this study, AEs will include events reported by the patient, as well as new onset abnormal findings on physical examination or laboratory evaluation. A new illness, symptom, sign or laboratory abnormality outside the range of normal limits or greater than 50% increase from baseline value if the baseline is above the upper limit of normal or worsening of a pre-existing condition or abnormality is considered an AE.

All AEs, including clinically significant abnormal findings on laboratory evaluations, regardless of severity, will be followed until satisfactory resolution. AEs should be reported up to 30 days following the last dose of study drug.

An abnormal laboratory value will be considered an AE if the laboratory abnormality is characterized by any of the following:

- Results in discontinuation from the study
- Is associated with clinical signs or symptoms
- Requires treatment or any other therapeutic intervention
- Is associated with death or another serious adverse event, including hospitalization.
- Is judged by the Investigator to be of significant clinical Impact

If any abnormal laboratory result is considered clinically significant, the investigator will provide details about the action taken with respect to the test drug and about the patient's outcome.

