### **9.2.2 NCI-IRB Requirements for PI Reporting of Adverse Events at Continuing Review**

The protocol PI will report to the NCI-IRB:

1. A summary of all protocol deviations in a tabular format to include the date the deviation occurred, a brief description of the deviation and any corrective action.
2. A summary of any instances of non-compliance
3. A tabular summary of the following adverse events:
  - All Grade 2 **unexpected** events that are possibly, probably or definitely related to the research;
  - All Grade 3 and 4 events that are possibly, probably or definitely related to the research;
  - All Grade 5 events regardless of attribution;
  - All Serious Events regardless of attribution.

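### Section 5.1.1 makes attribution to Eovist the test for recording AEs outside scanning sessions, in conflict with 9.1.1 and 5.1.2, and the two SAE rules in 5.1.2 leave the role of causality unclear

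*Combined protocol and SAP*

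**What the plan says.** Section 5.1.1 gives two recording rules for AEs. The first has no attribution limit: "Adverse events occurring during any scanning session will be recorded". The second does: "Adverse events which are designated possibly, probably or definitely related to Eovist® will also be recorded".

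Section 5.1.2 lists AEs among the safety data to be collected under the Study Calendar and sets no attribution limit. The calendar marks AE monitoring in the post-MRI column. Section 5.1.2 then gives two bullets for recording SAEs: "After a subject first received Eovist® and throughout the subjects follow-up period", and "During the subject's follow up period, and for which a causal relationship to Eovist® cannot be ruled out". It does not say whether the bullets are alternatives or joint conditions, and it does not define the follow-up period.

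Section 9.1.1 counts an event as an AE "whether or not the event is considered related to the treatment or clinically significant requiring treatment" and sets the window: "AEs should be reported up to 30 days following the last dose of study drug". It also has all AEs followed until they resolve.

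The continuing-review table in 9.2.2 is mixed. Grade 2 unexpected events and Grade 3-4 events are needed only if at least possibly related to the research. Grade 5 events are needed whatever their attribution, and so are serious events: "All Serious Events regardless of attribution".

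**The concern.** Attribution is a judgement about an event that is already on record. Section 5.1.1 instead uses it as a condition for making the record. A non-serious event judged unrelated and never entered cannot be re-judged later. That matters here because the study is open-label and single-center, the principal investigator and research nurse monitor AEs, and 9.3.1 states that there is no formal data and safety monitoring plan. Section 10.2.2 says that delayed reactions can appear hours to several days after the injection, which is when the 5.1.1 condition applies.

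The condition also names the wrong exposure for the 9.2.2 table. Section 5.1.1 asks about Eovist, whereas 9.2.2 asks about the research, which in the advanced arm can include a biopsy done for the study.

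**Working it through.** No plan figure needs reproducing. The check sets the recording rules (5.1.1, 5.1.2) beside the requirements (9.1.1, 9.2.2), by type of event.

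1. **Any AE during a scanning session.** Recorded under 5.1.1 whatever the attribution. No conflict.
2. **Non-serious AE after scanning, judged related to Eovist.** Recorded under 5.1.1. No conflict.
3. **Non-serious AE after scanning and within 30 days, judged unrelated to Eovist** (for example, a day-3 rash called unlikely related). It is an AE under 9.1.1 and falls under the unrestricted AE item in 5.1.2, but neither rule in 5.1.1 covers it. The instructions conflict. If staff follow 5.1.1, the event is not recorded.
4. **Non-serious Grade 3-4 event, or unexpected Grade 2 event, caused by the research biopsy and not by Eovist.** The 9.2.2 table asks for it because it is related to the research. Section 5.1.1 does not record it because it is not related to Eovist. Section 3.1.3.1 describes the advanced-arm biopsies as research biopsies, and the Study Calendar allows them until just under 20 weeks after the MRI. 20 x 7 = 140 days, and 140 - 30 = 110 days, so up to about 110 days of the biopsy period lie beyond the 9.1.1 window. A late biopsy complication therefore falls outside that window too.
5. **SAE or death after dosing, judged unrelated.** Section 9.2.2 requires it. If the 5.1.2 bullets are alternatives, the first captures it within the follow-up period and the second adds nothing. If both must be met, the second excludes it. Because the follow-up period is undefined, how long either rule applies is also open.
6. **SAE judged related to Eovist.** It satisfies both bullets, so it is recorded on either reading.

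Types 3 and 4 are gaps under 5.1.1 as written. Type 5 is a gap on only one of two readings.

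**The case against.** The strongest reply is that 5.1.1 says related events will also be recorded, not that only those will be, and that 5.1.2, the dedicated safety section, lists AEs without a limit. On that view the event in type 3 is subject to inconsistent instructions and is not clearly excluded. This is fair as far as it goes. But the second sentence of 5.1.1 would have no function if all AEs were recorded anyway, and staff who follow it would lose events that 9.1.1 covers.

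The reply is stronger against several wider readings that a reader might adopt:

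- **That the database cannot supply the 9.2.2 tables.** This is not shown. The Grade 2 and Grade 3-4 rows are limited to related events by design, and 5.1.1 supplies the Eovist-related part. The Grade 5 and serious rows can be filled from the first SAE bullet if the bullets are alternatives. Deaths not due to progressive disease also reach the IRB under 9.2.1.
- **That 5.1.2 definitely drops unrelated SAEs.** An unrelated hospitalization at day 20 is recorded under the first bullet, taking day 20 to be within follow-up. It is lost only if both bullets must be met.
- **That the stopping rule is starved of events.** The rule in 9.3.1 counts Eovist-related SAEs, and those are recorded on any reading. Dependence on the attribution call is built into the rule and would remain after the fix.
- **That nearly all of the 30-day window falls after the 60-minute scan, so nearly all events are affected.** That compares clock time, not events. Section 10.2.2 says most hypersensitivity reactions occur within half an hour.

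It can also be said that safety is not a listed objective and that each subject receives one dose of an approved agent. That limits the consequence but does not reconcile the sections.

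**Conclusion.** The conflict between 5.1.1 and 9.1.1, and between 5.1.1 and the AE item in 5.1.2, is real and should be corrected. Two classes of non-serious event may go unrecorded: those judged unrelated to Eovist within 30 days of dosing, and those related to the research biopsy but not to Eovist. The SAE wording in 5.1.2 is an ambiguity, with a loss against 9.2.2 only if both bullets must hold.

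The size in events is unknown, because the documents give neither a rate of unrelated AEs nor a rate of biopsy complications. The ceiling on evaluable subjects is 25, as in the Precis and 7.1 (3.1 says twenty). The biopsy gap concerns only those advanced-arm subjects who have a research biopsy, and that number is not stated. The conclusion assumes that 5.1.1 governs what is entered in C3D, which is how that section reads.

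**What to change.** In 5.1.1, replace the two AE sentences with one rule: all AEs meeting 9.1.1 within the reporting window are recorded in C3D, with grade and attribution as data fields. Assess attribution to the research, meaning Eovist and the research biopsy, so that it matches 9.2.2. State that research-biopsy events are recorded even when the biopsy falls after day 30.

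In 5.1.2, merge the two bullets into one rule that records all SAEs from Eovist administration through a defined follow-up period, whatever the attribution. Do not add a relatedness limit for SAEs after day 30. Section 9.2.2 has no such cut-off for serious events, and the first bullet runs throughout follow-up, so a limit could narrow what is captured now.

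Attribution then serves the 9.2.2 categories and the 9.3.1 count without deciding what is recorded. The cost is a few edited sentences and minor extra data entry for 25 subjects.

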### **3.1.3 Pathology**

#### **3.1.3.1 Surgical Pathology**

[figure not shown]
[figure not shown]
For the localized disease arm, biopsy specimens obtained from intraprostatic lesions or prostatectomy specimens will undergo standard preparation and sectioning in the Laboratory of Pathology for pathological diagnosis. The biopsy procedures for the localized disease arm will be part of standard of care.

For the advanced disease arm, biopsy specimens obtained from distant lesions will undergo standard preparation and sectioning in the Laboratory of Pathology for pathological diagnosis. The biopsy procedure for the advanced disease arm will be research biopsies and will be performed under imaging (ultrasound or CT) guidance.

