### 3.6 Study Calendar

The timing of study events in the following descriptions is relative to the administration of EOVIST®.

Procedure	Screening a	Baseline b	MR imaging			Scheduled Post-MRI c
			Just prior to MRI	Pre-injection MRI scan	Post injection MRI scan	
Informed consent	X					
Study entry criteria	X					
Demographic information	X					
Medical history and concurrent diseases	X					
Prior/concomitant medications	X					
Injection site monitoring				X	X d	X
Vital signs	X	X			X e	
Acute Care Panel, Hepatic Panel, Mineral Panel, PSA, & CBC	X f					
OATP1B3 Genotype analysis	X g					
Biopsy specimen available for OATP1B3 expression	X h, i					
Intravenous line started			X			
Eovist® injection				X		
Adverse Event Monitoring			X	X	X	X
MR Imaging				X	X j	
Biopsy Procedure						X k, l
Prostatectomy						X m
OATP expression and Comparative Analyses						X

a: Within 21 days of administrations of Eovist®

b: The day of MR imaging until just prior to administration of Eovist ®

- c. Timing of events is relative to administration of Eovist®
- d: 5 minutes post-Eovist® injection
- e: At the end of all scanning
- f: Clinical blood sample assessments must be performed within 21 days prior to administration of Eovist®.
- g: Will be performed at [name] Lab.
- h: For the localized disease arm, existing pathologic tissue (obtained <20 weeks before Eovist MRI) will be screened to see if it can be linked to MRI visible lesion in the patient candidate for Eovist MRI. Otherwise the tissue obtained from image guided biopsy (standard of care) at NCI will be used for OATP1B3 expression.
- i: For the advanced disease arm, availability of the previously (<20 weeks) obtained clinically acquired tissue will be checked.
- j: Immediately, 10, 20, & 60 minutes post-Eovist® injection
- k: To be conducted within <20 weeks after Eovist® enhanced MRI
- l: This applies for the advanced disease arm and will be conducted from a soft tissue or metastatic bone lesion (measuring  $\geq 1.5\text{cm}$  in diameter).
- m: This applies for the localized disease arm and will serve as a source of tissue only if previously acquired biopsy (confidently linked to an MRI visible lesion) or image guided standard of care biopsy at NCI will not be available.

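### The rules for recording complications of the advanced-arm research biopsy are inconsistent: non-serious events after day 30, and events after biopsy-triggered removal, have no clear capture

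*Combined protocol and SAP*

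**What the plan says.** **Status of the biopsy.** Section 3.1.3.1 states: "The biopsy procedure for the advanced disease arm will be research biopsies and will be performed under imaging (ultrasound or CT) guidance". Section 3.5.2 agrees. Section 3.7 describes all subjects alike: "As part of their standard of care for their disease, subjects will have biopsy within 20 weeks of Eovist® enhanced MRI".

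**Timing.** Footnote k of the Study Calendar (3.6) reads: "To be conducted within <20 weeks after Eovist® enhanced MRI". Section 3.6.1.4 gives the same limit. Subjects with suitable tissue taken clinically before the MRI do not need this biopsy.

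**What is recorded.** Section 5.1.1 names two classes of AE. The first is events during a scanning session. The second is given as: "Adverse events which are designated possibly, probably or definitely related to Eovist® will also be recorded". Section 5.1.2 collects AEs according to the Study Calendar and has two bullets on SAEs. The first runs from Eovist through follow-up with no condition on cause. The second is limited to events where Eovist cannot be excluded as a cause. The follow-up period is not defined.

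**For how long.** Section 9.1.1 says: "AEs should be reported up to 30 days following the last dose of study drug". Section 3.3 provides for one dose only.

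**When the subject leaves.** Section 3.9.1 lists as a removal criterion: "Subject completes Eovist® enhanced MRI and has biopsy of the target lesion".

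**What must be reported.** For continuing review, 9.2.2 requires a table that includes "All Grade 3 and 4 events that are possibly, probably or definitely related to the research". It also asks for unexpected grade 2 events related to the research, and for all grade 5 and all serious events whatever their attribution.

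**The concern.** The recording rules are built around the contrast agent and the scan. For a subject who needs it, the most invasive thing the study itself requires is the biopsy, which comes later and has complications of its own. Three rules work against recording them: attribution in 5.1.1 is to Eovist, the clock in 9.1.1 starts at the Eovist dose and never restarts, and 3.9.1 allows removal at about the time biopsy complications would begin. No visit or contact after the biopsy is described.

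Two things are at stake. The safety summary could look cleaner than the study was, because it would mainly reflect contrast and scan events. The 9.2.2 table, which is defined by relation to the research, would also rest on data that 5.1.1 does not tell staff to collect. The contradiction between 3.7 and 3.1.3.1 adds to this: staff who take the biopsy to be standard of care have less reason to call a complication research-related. Sections 8.1 and 8.3 expect no direct benefit to subjects, which makes a full account of research harms more important.

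**Working it through.** The plan gives no figure on this point to reproduce. The check compares the time windows and then takes each kind of event through the rules.

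**Step 1: windows.** Inputs are the 20-week limit (3.6, footnote k), the 30-day limit (9.1.1) and the single dose (3.3). Dose and MRI fall in the same session, so both clocks start together.

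- Permitted biopsy window after the MRI: 20 × 7 = 140 days.
- Part outside the AE window: 140 − 30 = 110 days.
- Share of the window: 110/140 = 0.786, or 79%.
- A biopsy on day d ≤ 30 has 30 − d days of AE reporting left. For d = 20 that is 10 days; for d = 30 it is none.

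**Step 2: which rule catches which event.**

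| Biopsy complication | Rules that apply | Result |
|---|---|---|
| Non-serious, within 30 days of dosing, still on study | 9.1.1 includes it whatever its cause; 5.1.1 does not name it | Rules conflict |
| Non-serious, after day 30 | 5.1.1 does not name it; 9.1.1 has closed; the SAE bullets of 5.1.2 do not apply; the calendar marks AE monitoring but gives no time | No clear capture |
| Serious, still on study | 5.1.2 first bullet includes it; second bullet requires possible Eovist causality; follow-up period undefined | Ambiguous |
| Arising after removal under 3.9.1 | No visit or contact described; 9.2.1 and 9.2.2 require some events to be reported if they become known | No clear capture |

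**Step 3: recording against reporting.** The 9.2.2 table is defined by relation to the research and includes non-serious events: unexpected grade 2, and grade 3 and 4. The second and fourth rows above can contain such events. For those rows, the reporting duty has no matching collection rule.

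**Step 4: who is affected.** Only advanced-arm subjects without usable prior tissue. The Precis and 7.1 plan 15 evaluable subjects in that arm and 3.1 plans 10, so the ceiling is 15. The documents do not say how many will need the biopsy.

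**Illustration only.** The documents give no biopsy complication rate. If all 15 subjects were biopsied and the rate of any complication were 1%, 5% or 10% (assumed), the chance of at least one would be 1 − 0.99^15 = 14%, 1 − 0.95^15 = 54% or 1 − 0.90^15 = 79%. With 10 biopsies the figures are 10%, 40% and 65%. These are chances that a complication occurs, not that it is missed. The last 79% has no connection with the share of the window in Step 1.

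**The case against.** The strongest reply is that 5.1.1 is headed Clinical Data and that safety data are governed by 5.1.2. That section makes the Study Calendar operative for AEs, and the calendar marks AE monitoring in the Scheduled Post-MRI column, which also holds the biopsy. The first SAE bullet in 5.1.2 sets no condition on cause. Section 9.1.1 defines AEs whether or not they are related to the treatment. Deaths not due to progressive disease and unanticipated problems go to the IRB under 9.2.1. Under 9.3.1 the investigator reviews AE data on each patient. Removal is also barred until unacceptable toxicities have settled.

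Much of this stands. A reader might infer that biopsy complications go wholly unrecorded, or that the 9.2.2 table cannot be completed. The documents do not support either: serious events have a possible route, and events of any cause within 30 days of dosing fall under 9.1.1.

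The reply does not close the gap, however. The calendar mark carries no time, and the matching text in 3.6.1.4 describes a single AE assessment, at the end of the 60-minute scan and so before the biopsy. The follow-up period in 5.1.2 has no stated end, and its two SAE bullets disagree on causality. The bar on removal follows a bullet that refers to 10.2.2, which concerns Eovist. The routes in 9.2.1 do not reach an expected, non-serious complication.

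A reader might also take 79% as the share of biopsies done after AE reporting closes. That would need biopsies spread evenly over the window, which nothing in the documents suggests. The condition of no intervening therapy (3.1) and the bar on delaying radiotherapy (2.1.2.8 and 3.8) point towards earlier biopsy.

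**Conclusion.** The plan is wrong as written on this point and should be fixed. Its rules conflict on whether, and for how long, complications of the research biopsy are recorded. Followed as they stand, they give no clear capture of non-serious complications after day 30 or of events arising after the biopsy has led to removal. For serious events the text is ambiguous rather than silent.

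The size is 110 of 140 days (79%) of the permitted window, in at most 15 evaluable subjects. The share is a property of the window and needs no assumption about when biopsies take place. The number of subjects depends on how many lack usable tissue, which is unknown.

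The primary analysis of signal change and the sample size are not affected. The stopping rule in 9.3.1 counts only Eovist-related SAEs. A reader might treat that as part of the same fault, but it is a design choice and no part of this conclusion.

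**What to change.** Reconcile 3.6, 3.7, 3.9.1, 5.1.1, 5.1.2, 9.1.1 and 9.2.2:

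- **5.1.1:** record AEs related to Eovist or to any research procedure, and name the research biopsy.
- **5.1.2 and 9.1.1:** define the follow-up period and the AE window from the research biopsy as well as from Eovist, and make the two SAE bullets agree on causality.
- **3.6:** give the AE-monitoring entry in the post-MRI column a time that matches.
- **3.9.1:** for biopsied advanced-arm subjects, set the off-study date at the end of the biopsy window. Its length and the form of contact are for the sponsor to decide.
- **3.7:** limit the standard-of-care statement to the localized arm, so that it agrees with 3.1.3.1 and 3.5.2.
- **Reporting:** show biopsy-related and Eovist-related events separately.

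The cost is a short amendment, one brief follow-up contact per biopsied subject, and slightly later off-study dates.
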